Pre-Analysis Plan for Endline Data in

the Indian Health Insurance Experiment (amended)

Note: This version amends the original version, posted March 14, 2019. The original, time-stamped version is available at

<https://www.socialscienceregistry.org/trials/1793>.

[name]*, [name]†, [name]‡,
[name]§, [name]¶,
[name]|| and [name]**

June 24, 2019

Abstract

We present the analysis plan for the Indian Health Insurance Experiment (IHIE). The IHIE is a randomized controlled trial examining the impacts of expanding Rastriya Swasthya Bima Yojana (RSBY), India's first large, national public health insurance program. RSBY is an insurance plan that covers INR 30,000 of hospital expenses per year for a family of up to 5 individuals. Begun in 2013, the IHIE randomized roughly 11,000 above poverty line (APL) households in two districts of Karnataka into four treatment arms that provided different levels of access to RSBY. The four arms were: (A) free RSBY, (B) access to RSBY for roughly INR 200 plus an unconditional cash grant of INR Rs. 200, (C) access to RSBY for roughly INR 200 (the premium for RSBY), and (D) no intervention. The study also randomized the fraction of villages within each arm to address spillover effects. We examine impacts on insurance uptake, utilization, finances (including out-of-pocket expenses), and health. We present the questions we address, the outcomes of interest, and our econometric strategy.

Contents

1	Introduction	3
2	Funding, ethical approval, and trial registration	5
3	Evaluation questions	5
4	Intervention	6
4.1	Context	6
4.2	RSBY	6
4.2.1	Access to RSBY	7
5	Evaluation Design	7
5.1	Sampling Strategy	7
5.2	Treatment assignment	8
5.3	Data Collection	8

*University of Chicago, [contact].

†University College London, [contact].

‡Harvard University, [contact].

§Tufts University, [contact].

¶University of Chicago, [contact].

||Public Health Foundation of India, [contact].

**University of Chicago, [contact].

5.3.1 Listing	9
5.3.2 Baseline Survey	9
5.3.3 Enrollment Survey	9
5.3.4 Post-health Event Survey (PHES)	9
5.3.5 Midline Survey	9
5.3.6 Endline Survey	9
5.4 Treatment Delivery	10
5.5 Balance Tests	10
5.6 Sample Attrition	10
5.6.1 Baseline attrition	10
5.6.2 Midline attrition	11
6 Companion willingness-to-pay study	11
7 Identification Strategy	11
7.1 Intent-to-Treat (ITT)	11
7.2 Complier average treatment effect (CATE)	13
7.3 Testing for heterogeneous effects	13

RSBY just assumed greater significance with the government’s announcement to use the program as a platform to move towards UHC. On February 1, 2018, the Union Budget announced the National Health Protection Scheme (NHPS), popularly known as “Modicare”, after PM Narendra Modi. Prime Minister Modi reiterated that it was a government priority in his Indian Independence Day speech on August 15, 2018. As of November 1, 2018, 33 states have agreed to implement the scheme.

If successful, the NHPS will extend health insurance to 500 million people from financially vulnerable households, nearly one-half India’s 1.2 billion population.¹ To put that in perspective, when the United States rolled out the Affordable Care Act (ACA) in 2010, the goal was to extend health care to nearly 50 million people, roughly one-sixth of its 320 million population. The success of Modicare—and other related insurance expansions—depends crucially on whether people sign up for the service, whether they use it, whether hospitals participate, and the value of medical care. Our project can help providing timely answers to many of these questions.

Our Project. The Indian Health Insurance Experiment (IHIE) is a large-scale, impact evaluation of expanding eligibility for RSBY. We also wish to estimate the health and financial impacts of health insurance in a low-income setting. Towards this end, the IHIE randomizes roughly 11,000 households (50,000 individuals) in the Indian state of Karnataka to four different methods of providing access to insurance: (A) free RSBY, (B) access to RSBY for roughly INR 200 plus an unconditional cash grant of INR Rs. 200, (C) access to RSBY for roughly INR 200 (the premium for RSBY), and (D) no intervention. In order to address potential spillovers between insured and uninsured households, we employ a two-stage design that randomized villages to different allocations across arms (A) – (D) before we randomize households to those four arms.

Use of this Pre-analysis Plan. This document provides a statistical analysis plan for data from the endline survey conducted roughly 4 years after treatment (and described in Section 5.3.6). The purpose is to commit to an analysis plan prior to obtaining endline data. As such, the document will be posted at the AEA trial registration site before we begin surveying sample households in the endline survey.

In the Appendix, we will explain how this Pre-Analysis Plan influences our analysis of data from two previously conducted surveys—a 12 month follow-up called the Post-Health Event Survey (PHES, Section 5.3.4) and an 18 month follow-up called the midline (Section 5.3.5).

Related Literature. There is a vast literature on evaluating health insurance expansions in developed and developing countries, using both experimental and quasi-experimental designs.

Although insurance has a myriad of effects, here we focus on two categories.² Insurance lowers the price of medical care on the margin. This has two effects. First, decisions to take care are inframarginal, i.e., are unchanged by the presence of insurance. For these events, insurance reduces the cost of care. This is manifest as lower out-of-pocket (OOP) spending. This can be unpacked depending on how individuals finance OOP spending; for example they could take out a loan or tap savings, they could sell an asset, or they could defer consumption. Each channel has a different welfare cost.

¹NHPS also expands RSBY on another margin besides eligibility: it expands the services covered. Whereas RSBY only covered short term treatments at acute care facilities (secondary hospital care), NHPS will also cover longer term treatments at hospitals (tertiary care). The latter is the sort of care covered in programs such as Arogyashree Vajpayee in Andhra Pradesh and Karnataka. This expansion in vertical coverage is also reflected in the annual caps for households, which will rise from the INR 30,000 under RSBY to INR 500,000 under NHPS.

²There are a number of other consequences of insurance. For example, if it is subsidized either by the government or via pricing regulations such as community rating, it may have so-called *ex ante* moral hazard effects, i.e., it may encourage risky health behaviors because it reduces the financial cost of sickness. Moreover, it may have spillover effects on local credit markets as it is a substitute for savings and borrowing as method of financing care.

Second, the lower price can lead to increased consumption of insured medical care, due to both substitution effects and income effects. It is possible for this care to be excessive, i.e., moral hazard, in the sense that an individual consumes more than they would were they charged the marginal cost of care. There are also income effects from insurance. If this marginal care that is purchased with insurance is productive, in the sense that it improves health care outcomes, we will see improvements in health due to insurance.

The degree to which there are effects on inframarginal and marginal consumption—and their knock-down effects—depends on a number of factors, including demand elasticity and how individuals finance medical care in the absence of the insurance being provided as treatment. For example, if individuals have informal insurance or free access to public hospitals, formal insurance or insurance that covers private providers, respectively, may yield no increase in utilization and thus health because it was merely replacing one method of insurance-like financing with another that covers private care.

Evaluating insurance is made more difficult due to selection into insurance. For example, adverse selection (advantageous selection) of higher (lower) risk individuals into insurance may cause those that are insured to appear less (more) healthy than those who are uninsured, even if insurance does not cause a reduction (an increase) in health. To address this problem, a number of experiments have been conducted that randomized individuals to access to insurance or insurance itself.

We can divide these experiments by whether they were conducted in high-income countries or not. In the U.S., two notable experiments are the RAND health insurance experiment (Newhouse, 1993) and the Oregon Health Insurance Experiment (OHIE) (Finkelstein et al., 2012). Both experiments find that there was an increase in utilization and a reduction in OOP payments due to insurance. However, RAND found that there were no significant health effects, though one could not rule out health effects for low-income populations. Likewise, OHIE found that Medicaid only had significant mental health effects (including for individuals who did not utilize care) and that one could not rule out effects on diabetes. A limitation of these studies for our research questions is that the health care and financing systems of high-income countries is different than those of low or middle-income countries. For example, the U.S. has a safety net, i.e., the Emergency Medical Treatment and Labor Act, state debtor-creditor laws, and bankruptcy, that less well-off countries may not have. This difference implies that insurance could have a larger impact in places like India. Conversely, less well-off countries may have a less developed health care infrastructure so that many individuals who are given insurance may not have access to facilities at which they can use insurance. This could lead insurance to have a lower impact in places like India.

Health insurance experiments have been conducted in China, Mexico, Cambodia, Nicaragua, Kenya, and India (reported in the next paragraph). A number have found that insurance did not increase utilization (and thereby did not impact health), but did reduce debt or catastrophic medical expenses (King et al., 2009; Levine et al., 2016; Thornton et al., 2010). This result may be due to care being inframarginal and insurance substituting one method of financing care for another. A recent experiment in Kenya, however, found no financial benefits from insurance either (Haushofer et al., 2017). That said, the study did find a "peace of mind effect" wherein individuals with health insurance experienced less stress, even if they did not use the insurance to obtain care.

Work on the impacts of health insurance in India is likewise mixed. Sood et al. (2014) evaluated the effects of a government insurance program covering tertiary care for BPL people in Karnataka (Vajpayee Arogyashree) using a geographic RD design (in 300 villages where the scheme was implemented and 272 neighboring matched villages). They found an increase in health care use, a reduction in mortality rates for covered conditions, and a decrease in OOP. Das and Leino (2011) randomized a pilot information and education campaign (IEC) in six (of 72) administrative circles in Delhi in 2008 (the year RSBY was launched), and found that the IEC campaign increased enrollment but decreased claim rates. Karan et al. (2017) used 3 waves of household level data from the National Sample Survey Organisation (NSSO) and district-level RSBY administrative data on enrollment, and found no effect on inpatient or outpatient expenditures, and a 30% increase in the likelihood of any OOP spending, using a difference-in-differences design. A recent review of the impact of publicly financed health insurance schemes (Prinjha et al., 2017) shows that, while all studies reviewed find an increase in the use of health services, only a few studies (in particular those evaluating state-sponsored health insurance schemes) find a reduction in OOP expenditures, with most of them finding no impact. Lastly, Ghosh and Gupta (2017) have recently shown that almost half of the households enrolled in RSBY actually belong to the non-poor category, and that RSBY had hardly any effect on financial protection. Importantly, to date, there has been no study evaluating the health impacts of RSBY.

When evaluating the impact of health insurance, it is important to acknowledge that prior to the introduction of formal insurance, villages may have had informal insurance (Townsend, 1994) or credit

markets to help people cope with health shocks. The introduction of formal insurance may impact the value of informal insurance or affect the operation of informal credit markets. For example, formal insurance may displace informal insurance (Attanasio and Rios-Rull, 2000; Dercon and Krishnan, 2003; Lin et al., 2014), or it may complement informal local insurance if it provides protection against aggregate village-level shocks that informal insurance cannot address (Dercon et al., 2014). Likewise, formal insurance may reduce demand for credit, pushing down interest rates for the uninsured, or it may reduce precautionary savings and thus credit supply, increasing interest rates for the uninsured. These potential spillovers will affect the overall value of insurance.

2 Funding, ethical approval, and trial registration

Funding. The IHIE was funded by the following entities, with earmarked funds indicated in parentheses:

- the University of Chicago via grants from the Law School, the Becker-Friedman Institute, the MacLean Center for Bioethics, and the Neubauer Collegium (for ethnographic work);
- Northwestern University;
- Department for International Development (DFID) (UK) via a grant to the Public Health Foundation of India (PHFI) (for baseline and part of treatment);
- the International Growth Centre (IGC) (for the 12 month follow-up, called the Post-Health Event Survey); and
- the Tata Trusts via a grant to the Tata Centre for Development (TCD) at the University of Chicago (for enrollment, the midline or 18 month follow-up, and endline or 4 year follow-up).

If a source is not followed by a parenthetical about how the funds were used, the funds from the source were not earmarked for a particular use.

Ethical approval. The study received IRB clearance at the University of Chicago (IRB12-2085), Northwestern University and Tufts University (during the periods [name] was at each institution), Princeton University and Harvard University (during the periods [name] was at each institution), University College London, University of Pennsylvania, PHFI, and the Institute for Financial Management and Research (IFMR). Presently, University of Chicago is the IRB of Record for the IHIE.

Trial registration. The IHIE was registered with the American Economics Association (AEA) Registry (RCT ID: AEARCTR-0001793) on December 16, 2016 (before the 18 month follow-up) and at ClinicalTrials.gov (ID: NCT03144076) on May 8, 2017. We did not register prior to these dates as it was not the norm in the economics literature to register experiments prior to initiation.

3 Evaluation questions

The IHIE was designed to address the following questions.

1. What is the value of health insurance in a developing country context? Specifically, what is the value of expanding eligibility for RSBY to the non-poor?

Within this broader question we address the following specific questions:

- (a) Does access to insurance or insurance itself increase utilization?
- (b) How does access or insurance affect health through increased utilization?
- (c) Does access or insurance affect health independent of utilization, perhaps through a "peace of mind" effect?
- (d) How does access or insurance affect a household's finances, its asset portfolio, its income, its consumption or the variability of its consumption through increased utilization?
- (e) Does access or insurance affect finances independent of utilization, perhaps by altering a household's portfolio and thus its income and consumption?
- (f) Is there an income effect from health care or health care financing (capital) costs?
- (g) Is there an income effect from health insurance premium subsidies?

When exploring these questions we address a number of other cross-cutting questions:

2. Do insurance prices affect utilization, and if so how?
3. Are there spillover effects on non-beneficiaries, or spillovers within beneficiaries?
4. Does access to insurance affect intra-household allocation of resources? How are the benefits of health insurance distributed within the household?

4 Intervention

4.1 Context

Indians have access to both government and private medical providers. The government operates a large number of facilities, from Primary Health Centres and Sub-Centres to District Hospitals. In addition, private doctors have offices and clinics, and there are private hospitals of various sizes. The government facilities largely offer free care, though they may not cover all populations and the quality has been questioned. Private facilities will often request at least a down payment before providing service and, in some cases, do not release the patient until the negotiated bill is paid in full. Overall, India faces a shortfall in supply in providers. For instance, 47% of children live in villages without any health facility at all (Ma and Sood, 2008).

Aside from RSBY, there are a limited set of insurance options in India. As previously stated, treatment at government facilities is largely free. In addition, the central government operates a scheme called Janani Suraksha Yojana (JSY) that provides cash payments to mothers who deliver in an institutional setting (as opposed to their homes). Some state governments have provided insurance programs that cover tertiary care (e.g., Arogyasri in Andhra Pradesh and Vajpayee Arogyashri in Karnataka). In addition there are private insurance options, often provided by employers, including the government for its employees.

In the areas of Karnataka where this study takes place, there are typically no insurance options aside from RSBY, Arogyashri Vajpayee, and a plan called Yeshasvini, which is only available to members of certain occupational cooperative societies (i.e., trade associations).

4.2 RSBY

RSBY was introduced in 2008 to provide hospitalization insurance to India's poor. Like Medicaid in the U.S., it is largely free to enrollees and is designed and largely funded by the national government, but administered by the state governments.

Eligibility. All households carrying BPL ration cards or those with members in certain occupations³ are eligible for RSBY. In addition states can expand eligibility to other groups so long as they (as opposed to the central government) pay the full cost of these groups. The scheme covers up to five members of each enrolled household: the head of household, the spouse and up to three dependents⁴. The threshold to define a household as BPL is set at approximately INR 900/month in rural areas, and INR 1,100/month in urban areas in Karnataka.

Coverage. RSBY covers up to INR 30,000 per year per household for over 700 procedures at empaneled hospitals. The covered procedures largely include those that require an overnight stay at a hospital, though there are a number of so-called day surgeries that are also covered⁵. Child delivery is also included. There are no deductibles or co-pays. RSBY covers all pre-existing diseases and there is

³These include: 1. building and other construction workers registered with the welfare boards; 2. licensed railway porters; 3. street vendors; 4. MNREGA workers who have worked for more than 15 days during the preceding financial year; 5. beedi workers; 6. domestic workers; 7. sanitation workers; 8. mine workers; 9. rickshaw pullers; 10. rag pickers; and 11. auto/taxi driver. See http://www.rsbypolice.gov.in/about_rsbypolice.aspx.

⁴An exception is in the case of childbirth: the newborn is always covered even if five members of the household are already covered. This coverage continues until the renewal date, at which point the newborn is only covered if the household chooses to include it among the five that are covered. See http://www.rsbypolice.gov.in/faq_medical.aspx.

⁵These include: haemo-dialysis; parenteral chemotherapy; radiotherapy; eye surgery; lithotripsy (kidney stone removal); tonsillectomy; D&C; dental surgery following an accident; surgery of hydrocele; surgery of prostate; few gastrointestinal surgery; genital surgery; surgery of nose; surgery of throat; surgery of ear; surgery of urinary system; treatment of fractures/dislocation (excluding hair line fracture), contracture releases and minor reconstructive procedures of limbs which otherwise require hospitalization; laparoscopic therapeutic surgeries that can be done in day care; identified surgeries under general anesthesia; and any disease/procedure mutually agreed upon. See http://www.rsbypolice.gov.in/faq_medical.aspx.

no age limit for beneficiaries. The rates of most surgical procedures are fixed⁶. Transportation charges are also covered at a rate of INR 100 per hospitalization up to a maximum of INR 1,000 per year. The coverage lasts one year starting the month after the first enrollment in a particular district, but is often extended without cost to beneficiaries.

Administration. RSBY is a completely paperless program which uses biometric-enabled smart cards as a vehicle of delivery. Empaneled hospitals include both private hospitals and government hospitals that meet certain criteria and sign MOUs with the state agency running the scheme; by implication, not all public hospitals are included. Insurance is provided by private companies, but the premium is paid for by the government. Government funding is shared by the central and the state government in a 3:1 ratio. The insurance premium is determined at the state-level based on an open-tender process. (The premium costs approximately INR 200 in the state of Karnataka). The only cost to the beneficiary is that of a registration charge of INR 30 to obtain the smart card.

4.2.1 Access to RSBY

We evaluate three methods of accessing RSBY:

- A. Free RSBY. Households obtain access to RSBY for no charge, not even the INR typically charged to obtain a biometric, smart card that functions as the insurance card.
- B. Right to purchase RSBY and an unconditional cash transfer equal to the premium. Households obtain an unconditional cash transfer equal to the RSBY premium in their district plus the right to buy RSBY in the following 3 weeks.
- C. Right to purchase RSBY. Households receive the right to buy RSBY in the next 3 weeks, but no cash transfer, conditional or otherwise.

We compare outcomes under these conditions versus a control condition:

- D. No intervention.

We choose these interventions because they address important academic and policy questions. Programs such as RSBY in India or Medicaid in the US are actually two conceptually distinct interventions: access to insurance at full price (i.e., pure insurance) and a (conditional) cash transfer equal to the insurance premium. Moreover, different interventions have different budgetary effects; we want to net these out by comparing budget neutral alternatives such as conditional and unconditional cash transfers. We seek to value each of these interventions. These not only have different effects, they are different policy options available to the government. Comparing condition C to condition D yields the value of pure insurance. Comparing condition A to C yields the value of a conditional cash transfer. Finally, comparing conditions A and B yields the difference between a conditional and an unconditional cash transfer.

5 Evaluation Design

We carried out a randomized controlled trial (RCT) to test the impacts of the RSBY expansion to APL households.

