5.4 Treatment Delivery

The population that is eligible for this study would not be eligible for RSBY under the program's usual rules. To make this study possible, we exchanged letters of cooperation with the state in which we conducted the study (Karnataka), the central government agency (Ministry of Labor) responsible for administration of RSBY, and the development organization (GIZ) providing technical support for RSBY.

Sample households were randomized in August 2014 using data from the listing exercise. They were informed of their treatment assignment and, depending on which arm to which they are assigned, given access to insurance or cash in May and June 2015. This step took place roughly 18 months after the baseline due to government constraints. Due to challenges associated with evaluating a government program, we were only able to enroll sample households when the government held its RSBY enrollment drive in early 2015.

We enrolled study households much in the same way the government enrolled RSBY (non-study) eligible households into the program: via a mobile enrollment truck that visited each village. One difference is that we went to each household to ask them if they would like to enroll and took them to the enrollment truck, which was parked in one place in the village. By contrast, the government informed non-study households by delivering paper notices (chits) to each home about when and where the enrollment truck would be in the village.

Roughly 78.4%, 70.4% and 58.6% of households in arms A, B, and C, respectively enrolled in RSBY. Enrollment rates are somewhat higher in Gulbarga than Mysore: 77.9/76.4/64.1% v. 78.8/63.5/52.3% in A/B/C. No one in arm D enrolled.

For all study households that take up insurance, we paid the government their premiums. For households in arms A, this was funded by grant funds. For those in B and C that purchase insurance, this was funded by the respondents' money.

The Karnataka government renewed RSBY automatically for non-study and study households in 2016 and 2017 without any action—even payment—by enrollees. RSBY ended in the state on August 31, 2018, to make way for the new NHPS scheme, which is scheduled to start in late 2018 or early 2019. As of this writing, Karnataka had agreed to roll out NHPS but had not begun the roll-out.

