10.1 Higher price causes greater utilization

We test whether the midline finding persists at endline in two ways:

- We examine whether group C households have higher rates of attempts to use RSBY and successful efforts to use RSBY.
- Because households with more members have a lower effective price per member¹⁸, larger households should have greater utilization per capita (as opposed to per household).

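### Arm C paid one premium and was then renewed free twice, so C–D at midline and endline is not the value of insurance at full price, and A–C is a one-off premium waiver

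*Combined protocol and SAP*

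**What the plan says.** Section 4.2.1 splits a scheme such as RSBY into two parts: insurance sold at full price, which it calls pure insurance, and a conditional transfer worth one premium. Arm A gets cover free. Arm B gets cash equal to the premium and a three-week right to buy. Arm C gets only the right to buy. From this it concludes: "Comparing condition C to condition D yields the value of pure insurance". It reads A–C as the value of the conditional transfer. Neither reading is limited to a period.

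On price and term, Section 4.2 says: "The premium costs approximately INR 200 in the state of Karnataka". It adds: "The coverage lasts one year starting the month after the first enrollment in a particular district, but is often extended without cost to beneficiaries".

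Section 5.4 then reports what happened after enrolment: "The Karnataka government renewed RSBY automatically for non-study and study households in 2016 and 2017 without any action". It notes that enrollees did not pay for these renewals, and that "RSBY ended in the state on August 31, 2018".

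Section 3 asks, as question 1(g): "Is there an income effect from health insurance premium subsidies". Section 10.1 returns to the midline observation of higher card use in arm C: "We test whether the midline finding persists at endline in two ways". None of Sections 4.2.1, 7 or 10 carries the free renewals into the meaning of the contrasts.

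**The concern.** By the decomposition in Section 4.2.1, a year of cover that costs the household nothing is insurance plus a transfer. From the first renewal on, an enrolled arm C household held the same free cover as an enrolled arm A household. C–D measured over the whole period therefore contains a subsidy that the plan says it excludes. A–C covers one premium only, in 2015.

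Question 1 (the value of insurance), question 1(g) (premium subsidies) and question 2 (prices and utilisation) all draw on these contrasts. If Section 4.2.1 is followed literally, a midline or endline C–D estimate would be reported as the value of insurance at full price, although about two-thirds of the cover in that arm was free. A policymaker choosing between paid and free access would be given the wrong label for the effect.

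**Working it through.** The plan states no figure for this point, so there is none to reproduce. The check sets the price and timing statements side by side.

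**Inputs**
- Entry price in arms B and C: about INR 200, one three-week window (Sections 4.2 and 4.2.1).
- Access given in May and June 2015; renewed free in 2016 and 2017; scheme ended 31 August 2018 (Section 5.4).
- Term: one year from the month after first enrolment in the district (Section 4.2).
- Enrolment: A 78.4%, B 70.4%, C 58.6%, D none (Section 5.4).
- Surveys: PHES May–June 2016, midline November 2016–February 2017, endline March–May 2019 (Sections 5.3.4 to 5.3.6).

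**Assumptions**
- Cover starts in June or July 2015, the month after study enrolment. If the government drive had opened a district earlier, the paid part would be shorter and the free share larger.
- A renewal year is worth INR 100–300. The plan does not give the renewal-year premium.

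**Step 1: free share of cover**
- June 2015 start: 3 × 12 + (8 − 6 + 1) = 39 months. Free: 39 − 12 = 27, and 27/39 = 69%.
- July 2015 start: 3 × 12 + (8 − 7 + 1) = 38 months. Free: 38 − 12 = 26, and 26/38 = 68%.

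**Step 2: average price to an arm C enrollee**
- 200/(39/12) = INR 61.5 a year; 200/(38/12) = INR 63.2 a year.

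**Step 3: share of premium value paid by an arm C enrollee**, as 200/(200 + 2P), with P the value of a renewal year
- P = 100: 50%. P = 200: 33%. P = 300: 25%.
- This counts two renewal years and ignores the last two to three months, so it slightly overstates the share paid. No value in the range comes near full price.

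**Step 4: what randomisation still separates**
- Enrolment gaps: C–D 58.6 points; A–C 78.4 − 58.6 = 19.8 points.
- Free renewal per assigned household at P = 200: arm A 0.784 × 400 = INR 314; arm C 0.586 × 400 = INR 234. The difference, about INR 79, reaches A–C through enrolment.
- The documents describe no new offer to households that declined in 2015, and nobody in arm D enrolled. Renewal therefore did not close these gaps.

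**Step 5: position of the surveys**
- Midline was 16–20 months after cover began, past the first free renewal.
- Endline starts after cover has ended: September 2018 to February 2019 is six full months.
- PHES recall covers the two months before the screening call. With a July 2015 start, this lies inside the paid year. With a June start, the paid year ends in May 2016 and a window from a June call would straddle the boundary. The plan gives no renewal date by district.

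**The case against.** The strongest reply is that nothing in the analysis is invalid. The 2015 price was randomised, and the enrolment gap it produced lasted. Section 7.1 defines the intent-to-treat effect as that of different forms of access, and Section 7.2 instruments enrolment. The full-price language stands only where Section 4.2.1 explains the choice of arms. Free renewal is disclosed in Section 5.4, and Section 4.2 says extensions without charge are common. All of this stands. It limits the point to interpretation but does not make the quoted sentence correct.

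Four stronger readings are tempting, and the documents do not support them.

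- A reader might infer that A–C is void. Section 4.2.1 describes a transfer of one premium and never says it recurs. A–C still identifies a one-off waiver.
- A reader might infer that the price tests in Section 10 are empty. Selection, signalling and sunk cost turn on what households and their neighbours paid in 2015, and that still differed.
- A reader might infer that a null at endline would be misread because the price difference had ended in the meantime. The midline survey also came after the first free renewal, so the two surveys do not differ in this respect.
- A reader might put a percentage on how far C–D overstates full-price insurance. That needs a paid-renewal rate the plan does not give, effects proportional to cover, and no later purchase by households that declined in 2015. At 90% renewal, 0.586 × 0.10 = 0.0586 would drop out in a year. Purchase by 0.0586/0.414 = 14% of the uninsured would offset this fully. The size cannot be derived, and neither can the direction.

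It is also fair that a first-year-only analysis may not be feasible on a useful scale. PHES covers only households screened for serious sickness, and Section 8 lists no event dates for illness or treatment.

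**Conclusion.** The point holds as a correction of what the contrasts are said to mean. An arm C enrollee paid about INR 200 once for about 38–39 months of cover, 68–69% of it free. That is an average of about INR 62–63 a year, or 25–50% of the premium value if a renewal year is worth INR 100–300. The midline and endline C–D contrast is thus the effect of the 2015 offer with the free renewals that followed, and not the value of insurance at full price.

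A–C remains a valid estimate of a one-off waiver, together with the later free cover of the households that the waiver brought in. The price tests remain valid as tests of the entry price.

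The free share rests on the assumed start of cover in June or July 2015. The conclusion itself needs only the statements on free renewal and on the end date in Section 5.4.

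**What to change.** 1. In Section 4.2.1, define C–D as the effect of a one-time offer at about INR 200 followed by free renewals to August 2018. Define A–C as the effect of waiving the 2015 premium once, including the later free cover of households induced to enrol. State that midline and endline C–D will not be reported as the value of full-price insurance.
2. In Section 10.1, say that the endline comparison, like the midline one, tests the lasting effect of the 2015 entry price, because no arm faced a price at renewal.
3. Limit any full-price reading to outcomes that can be shown to fall within the first policy year, which means at most part of PHES. Label it secondary.

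Items 1 and 2 cost a few sentences. Randomisation, outcomes, estimators and tests stay as they are. Item 3 needs renewal dates by district and the timing of PHES events, and it would rest on a screened sample with a two-month recall, so it would be less precise and may prove infeasible. The real cost is that the main surveys can no longer be used to claim a full-price effect.
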